APPENDIX 5. MODERATE/STRONG CYP3A4 INHIBITORS AND CYP3A4 INDUCERS

Laquinimod pharmacokinetics are affected by moderate and strong CYP3A4 inhibitors; moderate/strong CYP3A4 inhibitors are disallowed within 2 weeks of baseline until 30 days after the last dose has been administered.

Moderate and strong CYP3A4 inhibitors are prohibited because concomitant administration is predicted to increase laquinimod exposure and may increase the likelihood of adverse events (Table 8).

Table 8: A Partial List of Moderate/Strong CYP3A4 Inhibitors Disallowed 2 Weeks Prior to and During the Treatment Period and 30 Days After Last Dose

Medication class	Drug name
Protease inhibitors	indinavir, saquinavir, lopinavir, nelfinavir, amprenavir, atazanavir, darunavir, ritonavir
Antivirals:	boceprevir, telaprevir, danoprevir, ledipasvir, elvitegravir
Antifungals:	ketoconazole, itraconazole, voriconazole, posaconazole, fluconazole
Antibiotics	troleandomycin, clarithromycin, telithromycin, ciprofloxacin, erythromycin
Antidepressant	nefazodone
Calcium channel blocker	diltazem, verapamil, mibepradil
Antiemetics	aprepitant, casopitant, netupitant
Diuretics	conivaptan
Antineoplastic agents	imatinib
Antiarrhythmics	dronedarone

Note:

- This is a partial list only
- Systemic drugs only. Topical preparations (vaginal preparations, creams, etc) are allowed.

Inducers of CYP3A4 are also disallowed during the study ([Table 9](#)).

Table 9: A Partial List of CYP3A4 Inducers

Medication class	Drug name
Antibiotics	rifampin, rifabutin, nafcillin
Anticonvulsants	phenytoin, carbamazepine, phenobarbital, oxcarbazepine
Antineoplastic agents	mitotane
Anti-retroviral	efavirenz, talviraline, etravirine, lersivirine
Protease inhibitors	lopinavir, tipranavir, ritonavir
Antilipemics agents	avasimibe
Antiandrogens	enzalutamide
Endothelin Receptor Antagonists	bosentan
Antipsychotics	thioridazine
Psychostimulants	modafinil, armodafinil
Herbal Medications	St. John's wort

APPENDIX 6. LIST OF MEDICATIONS THAT SHOULD BE USED WITH CAUTION

Laquinimod 0.6 mg/day increases the systemic exposure of midazolam (a sensitive CYP3A4 substrate) 1.5-fold. Therefore, plasma levels of drugs that are CYP3A4 substrates may increase when combined with laquinimod. Subjects taking drugs that are metabolized by CYP3A4 (specifically those with a Narrow Therapeutic Index) ([Table 10](#)) should be advised that plasma levels of these drugs could increase when combined with laquinimod.

Table 10: A Partial List of CYP3A4 Substrates with a Narrow Therapeutic Index

alfentanil
cyclosporine
diergotamine
ergotamine
fentanyl
pimozide
quinidine
sirolimus
tacrolimus

Laquinimod 0.6 mg/day reduces the systemic exposure of caffeine (a sensitive CYP1A2 substrate) 5-fold. Laquinimod doses higher than 0.6 mg/day may further increase CYP1A2 induction and decrease exposure of CYP1A2 substrates. Plasma levels of drugs that are CYP1A2 substrates may decrease when combined with laquinimod. Also, during a period of 30 days following the last laquinimod dose these CYP1A2 substrates are potentially less effective due to decreased plasma levels. [Table 11](#) presents a partial list of drugs that are mainly metabolized by CYP1A2, ie, CYP1A2 plays a major role in their biotransformation. The systemic exposure of these drugs is expected to be significantly reduced by laquinimod coadministration. Drugs that are mainly metabolized by CYP1A2 and have a narrow therapeutic index are of special concern and appear in bolded text.

[figure not shown]
In general, as a precautionary measure, it is recommended to avoid the use of CYP1A2 substrates in clinical trials of laquinimod. Therapeutic alternatives may be considered in the appropriate clinical context.

Table 11: A Partial List of Drugs that are Mainly Metabolized by Cytochrome P450 1A2

Medication class	Drug name
Antidepressant	Agomelatine, Duloxetine, Mirtazapine, Nortriptyline, Fluvoxamine
Antipsychotics	Chlorpromazine, Clozapine , Olanzapine, Thiothixene, Trifluoperazine
Migraine Treatments	Frovatriptan, Zolmitriptan
Anesthetics	Lidocaine (systemic use)
Antineoplastic agents	Erlotinib
Muscle relaxants	Cyclobenzaprine, Tizanidine
Sleep disorders	Melatonin, Ramelteon
Respiratory Agents	Aminophylline, Theophylline
Benzodiazepines	Chlordiazepoxide
Alpha adrenergic agonist	Guanabenz
Beta blockers	Propranolol
Parkinson's treatment	Rasagiline, Ropinirole
Alzheimer's Treatments	Tacrine
Diuretics	Triamterene
Miscellaneous agents	Alosetron (irritable bowel syndrome treatment), Riluzole (amyotrophic lateral sclerosis treatment), Methadone

Drugs with a narrow therapeutic index appear in bolded text

APPENDIX 8. LIST OF DATA SAFETY MONITORING BOARD (DSMB) MEMBERS

It should be noted that as the study is in open label phase, the originally assigned DSMB is not operating any further.

The study is supervised by Teva's internal safety committee as well as by an external Data Monitoring Committees (DMC) of the ongoing Phase III studies MS-LAQ-301 (ALLEGRO) and MS-LAQ-302 (BRAVO).

APPENDIX 9. LIST OF CLINICAL ADVISORY BOARD (CAB) MEMBERS

APPENDIX 10. GUIDANCE ON SAFETY MONITORING

1. Guidance on Monitoring Subjects with Elevated Liver Function Tests

Liver enzymes (ALT, AST, GGT, ALP), as well as total bilirubin^o will be measured at each study visit.

In any case of elevated ALT or AST to a level exceeding of $\geq 2 \times \text{ULN}$ (including subjects whose Baseline ALT or AST levels are $\geq 2x$ and $\leq 3x$ the ULN, who may be enrolled in the study), a thorough medical history and physical examination with a focus on liver disease should be undertaken^p. In addition, the subject should be instructed to refrain from alcoholic beverages.

In case of symptoms compatible with drug-induced liver injury, the subject should be invited for an unscheduled visit to measure liver enzymes as soon as possible.

Solitary elevations of total bilirubin, not accompanied by elevations of ALT or AST should be managed according to the discretion of the Study Physician/Neurologist.

1.1. Elevation of Either ALT or AST to $\geq 3 \times \text{ULN}$:

Confirmation of the abnormality (in case the abnormality is of ALT or AST ≥ 8 times the ULN, no confirmation is required prior to study drug discontinuation, but the assessments below should be performed):

- The day in which the abnormal value is received from the laboratory will be considered as Day 0.
- The Investigator should repeat the test before Day 2, for confirmation purposes (this may be performed in a local laboratory along with CBC and differential to assess for eosinophilia. In general, in case a blood sample is sent to a local laboratory, the following assessments [and reference ranges] are mandatory: ALT [serum glutamic pyruvic transaminase; SGPT], AST [serum glutamic oxaloacetic transaminase; SGOT], ALP, total bilirubin, CBC [with differential for eosinophil count, separate tube], and INR [separate tube; not to be sent in a confirmatory test]). The investigator should also question the subject regarding symptoms.

The abnormality will be regarded as confirmed in each of the following scenarios:

1. In case Baseline value was within normal range and ALT or AST is still $\geq 3 \times \text{ULN}$

^o In case total bilirubin is $>\text{ULN}$, than direct bilirubin will be checked

^p Thorough medical history with a focus on liver disease: Personal or family history of liver disease; personal history of a systemic disease with potential liver involvement; exposure to alcohol, medications (prescription or OTC), herbal preparations, dietary supplements, recreational drugs, special diets or environmental chemical agents; potential exposure to infectious agents (eg, travel to developing countries, history of potential exposure to blood or blood products, high-risk sexual relations) and any additional information deemed relevant by the investigator. Physical examination – including signs of chronic liver disease

2. In case Baseline value was above ULN and ALT or AST is ≥ 2 times the Baseline value.

Upon confirmation of the abnormality as noted above, the following additional evaluations should be performed and results should be recorded in the eCRF.

Additional Tests/Evaluations

- Serology for Hepatitis A, B, and C viruses (central laboratory).
- Serology for autoimmune hepatitis: anti-nuclear antibodies, ASMA (Anti Smooth Muscle Antibodies), anti-LKM (Liver Kidney Microsomal) antibodies (central laboratory).
- An ultrasound examination of the liver and biliary tract.
- Other diagnostic tests/consultations, as deemed necessary by the investigator e.g. serology for hepatitis E virus in case of travel to endemic geography)

Observation and Follow-Up (to be performed after the abnormality was confirmed as above)

1.1.1. ALT or AST $\geq 3 \times$ and $\leq 5 \times$ ULN (if Baseline value is $\geq 2.5 \times$ ULN, ALT or AST $\geq 3.5 \times$ ULN and $\leq 5 \times$ ULN)

In addition to the above procedures required for any elevation to levels $>3 \times$ ULN:

- ALT, AST, GGT, ALP, total and direct bilirubin, CBC and differential (to assess for eosinophilia) and INR should be monitored on days 5 (± 2), 8 (± 2), 14 (± 2), and 28 (± 2). On at least 1 of these days, the test should be performed centrally. (INR should be sent to a local laboratory only.)
- In cases where a local laboratory is used, the results should be recorded in the eCRF, accompanied by the reference range of the relevant measurements.
- Should the abnormality ($\geq 3 \times$ ULN in case Baseline within normal range or $\geq 2 \times$ ULN in case the Baseline value was above ULN, but still $< 5 \times$ ULN) persist further, the subject will be followed according to the investigator's discretion, but at least once a month a blood sample for ALT, AST, GGT, ALP, and total and direct bilirubin should be sent to the central laboratory.

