7.3.4.1. Safety Stopping Rules

7.3.4.1.1. Liver Enzymes

In any increase of ALT or AST to ≥ 2 times ULN the “Guidance on Safety Monitoring” (see [Appendix 10](#)) should be thoroughly followed.

In the following circumstances, study drug will be discontinued immediately and liver enzymes will be monitored according the guidance in [Appendix 10](#):

- Any increase in ALT or AST to ≥ 3 times ULN, combined with INR >1.5 or total bilirubin $>2\times$ ULN
- Any increase in ALT or AST to ≥ 3 times ULN, which is accompanied by nausea, vomiting, fever, rash, or eosinophilia
- Any increase in ALT or AST to levels ≥ 5 but <8 times ULN, which is persistent for ≥ 2 weeks of repeated measurements.
- Any increase in ALT or AST to levels ≥ 8 times ULN
- In any case where monitoring of liver enzymes cannot be performed according to the protocol guidance (see [Appendix 10](#))

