1.1.2. ALT or AST $\geq 5 \times$ but less than $8 \times$ ULN

In addition to the above procedures required for any elevation to levels $>3 \times$ ULN:

- ALT, AST, GGT, ALP, total and direct bilirubin, CBC and differential count (to assess for eosinophilia), and INR should be monitored twice a week.

- At least for every other measurement, the tests should be sent to the central laboratory. The rest of the tests may be sent to a local laboratory. INR should always be sent to a local laboratory.

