1.1.3. ALT or AST \geq 8xULN

In addition to the above procedures required for any elevation to levels >3 xULN:

- The study drug should be discontinued immediately and the early termination visit should be performed.
- For follow-up guidance, please see below section "*Follow-up of Liver Enzymes after Stopping-Rules are met*".

1.2. Stopping Rules:

In the following circumstances, the study drug will be discontinued immediately:

- Any increase in ALT or AST to $\geq 3 \times \text{ULN}$, combined with INR > 1.5 or total bilirubin $> 2 \times \text{ULN}$
- Any increase in ALT or AST to $\geq 3 \times \text{ULN}$, which is accompanied by nausea, vomiting, fever, rash, or eosinophilia
- Any increase in ALT or AST to levels $\geq 5 \times$ but $< 8 \times \text{ULN}$, which is persistent for ≥ 2 weeks of repeated measurements
- Any increase in ALT or AST to levels $\geq 8 \times \text{ULN}$
- In any case where monitoring of liver enzymes cannot be performed according to the protocol guidance

1.2.1. Follow-Up of Liver Enzymes After Stopping-Rules Are Met:

- A subject who meets the above criteria for discontinuation of the study drug should be invited to the site to return the study drug. Early termination visit activities should be performed as soon as possible.
- Liver enzymes should be monitored until normalization or stabilization of the abnormality, according to the discretion of the investigator.
- In any case, following early termination, the minimal follow-up period will be 4 weeks and will include measurement of liver enzymes at least QW (may be performed in a local laboratory, with at least 1 test being sent to the central laboratory).
- Every effort should be made to complete the additional tests/ evaluations, as described above.

2. Use of Moderate/Strong CYP3A4 Inhibitors

Laquinimod PK is affected by moderate and strong CYP3A4 inhibitors; therefore, moderate/strong CYP3A4 inhibitors are disallowed during study and 30 days after the last dose has been administered. A partial list of commonly used CYP3A4 inhibitors is presented in [Appendix 5](#).

3. Cancers diagnosed during the study

Subjects that are diagnosed with a malignant solid or liquid tumor while participating in the study should stop study drug.

4. Guidance on Monitoring Subjects with Elevated Pancreatic Amylase Levels

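### Appendix 10 keeps INR out of the confirmatory liver test, so for ALT or AST of 3 to below 8 times ULN the INR limb of the immediate-stop rule has no scheduled value at that draw

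*Combined protocol and SAP*

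**What the plan says.** Section 7.3.4.1.1 introduces its liver rules with "In the following circumstances, study drug will be discontinued immediately". The first rule applies to any rise of ALT or AST to at least 3 times ULN "combined with INR >1.5 or total bilirubin" above 2 times ULN. Appendix 10, 1.2, repeats the list under "In the following circumstances, the study drug will be discontinued immediately".

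INR measurement is governed as follows:

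- Section 8.2.5 lists INR as a local-laboratory test, run only if Appendix 10 calls for it.
- Appendix 10, 1.1, sets Day 0 as the day the abnormal value is received, then states: "The Investigator should repeat the test before Day 2, for confirmation purposes". Among the tests for a local sample it marks "INR [separate tube; not to be sent in a confirmatory test".
- The additional tests due on confirmation are viral and autoimmune serology, liver ultrasound, and others at the investigator's discretion. INR is not named.
- Appendix 10, 1.1.1 (confirmed 3 to 5 times ULN), asks for a differential count "to assess for eosinophilia) and INR should be monitored on days 5" (±2), and again on days 8, 14 and 28. It adds: "INR should be sent to a local laboratory only".
- Appendix 10, 1.1.2 (5 to below 8 times ULN), lists the same tests "and INR should be monitored twice a week", with no first day.
- Appendix 10, 1.1.3 (8 times ULN or more), stops the drug at once.

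**The concern.** INR above 1.5 is one of two alternatives in the first stop rule, so with ALT or AST at 3 times ULN it is enough by itself to stop the drug. The one document that can trigger an INR removes it from the first blood draw after the elevation is known. A site that follows the plan exactly cannot evaluate that limb at the confirmatory draw, and daily dosing continues until the first scheduled INR. No reason is given for the exclusion. At stake is a few days of continued dosing in a subject whose only stop signal is the INR.

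**Working it through.** **Timing, confirmed 3 to 5 times ULN**

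1. The plan's own figure: Day 5 (±2) gives Day 5 − 2 = 3 to Day 5 + 2 = 7.
2. The confirmatory draw is due before Day 2, that is on Day 0 or Day 1.
3. Daily doses between the confirmatory draw and the first scheduled INR:
   - nominal: 5 − 1 = 4 to 5 − 0 = 5
   - shortest: 3 − 1 = 2
   - longest: 7 − 0 = 7, which needs a Day 0 draw and the last day of the window together.
4. Assumptions: days are counted from Day 0, the only origin defined, and result turnaround is the same at both draws. If days were counted from a confirmation on Day 0 or 1, the first INR would fall on Day 3 to 8. Day 0 is receipt of the result, so the delay from the first abnormal sample is longer by a turnaround time that the documents do not state.

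**Timing, 5 to below 8 times ULN**

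The Day 3 to 7 figure does not carry over. If twice weekly means every 3 to 4 days from confirmation (assumption), the delay is up to about 4 doses.

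**Which criteria can be judged by the confirmatory draw**

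| Criterion | Available by then? | Source |
|---|---|---|
| Total bilirubin above 2 times ULN | Yes: each visit, and mandatory in a local repeat | Appendix 10, 1 and 1.1 |
| Nausea, vomiting, fever, rash | Yes: subject is questioned at confirmation | Appendix 10, 1.1 |
| Eosinophilia | Yes: differential in the visit panel and in a local repeat | Section 8.2.5; Appendix 10, 1.1 |
| INR above 1.5 | No scheduled value | Section 8.2.5; Appendix 10, 1.1 |

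The gap therefore concerns only a subject with INR above 1.5, bilirubin no more than 2 times ULN, no listed symptom and no eosinophilia.

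**How many subjects might need the tube**

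Table 4 (Section 3.4.1.1), laquinimod 0.6 mg, normal at baseline, peak above 3 and up to 8 times ULN:

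- ALT: (30 + 5)/888 = 3.9%
- AST: (9 + 1)/950 = 1.1%
- Either: 3.9% (full overlap) to 5.0% (no overlap)
- Applied to the 110 ongoing subjects (Section 21.1): about 4.3 to 5.5, so roughly 4 to 6

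This is a loose upper bound. Table 4 counts peak values that are not stated to be confirmed. It comes from studies of up to 2 years from treatment start, and elevations generally arose in the first 6 months. It also includes background elevations: on placebo, ALT in the same range is (5 + 6)/930 = 1.2%.

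**Exposure**

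With a half-life of about 80 h (Section 3.1.2) and mono-exponential decline (assumption), stopping at the confirmatory draw would leave 0.5^(96/80) = 44% of the drug level after 4 days, or 0.5^(120/80) = 35% after 5, instead of continued dosing. Nothing in the documents ties this difference to harm.

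**The case against.** The schedule is explicit and looks deliberate: confirm the abnormality first, then work it up, with INR in the second stage. The requirement to stop immediately governs action once a circumstance is known and sets no sampling time, so the plan does not contradict itself. Appendix 10, 1.1, lets the investigator add other diagnostic tests on confirmation, and Sections 7.3.6, 7.3.6.1 and 8.2.5.1 allow unscheduled testing. Already at 2 times ULN a liver-focused history and examination are required. Section 3.4 reports that Hy's law criteria were not met and that there was no liver failure. After Month 24 scheduled laboratory tests are six-monthly, so an elevation may predate Day 0 by months, beside which 4 to 5 days is small.

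Most of this stands and limits the weight of the point. Two parts do not answer it. The stop rule applies to any rise to 3 times ULN and does not wait for confirmation, so staging does not explain why its INR limb goes unmeasured. For example, with a baseline of 2 times ULN, confirmation under Appendix 10, 1.1, needs 2 × 2 = 4 times ULN; a repeat at 3.5 meets the enzyme part of the stop rule but triggers no scheduled INR. And the discretionary clauses permit an INR without requiring one, while the appendix tells sites not to send it with the confirmatory sample.

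A reader might infer that 4 to 6 subjects are at risk, or that subjects with liver injury are generally left on drug. The documents support neither. The count is a loose upper bound on who would need the tube, and the other stop criteria can be applied by the confirmatory draw.

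**Conclusion.** The point holds as a narrow, low-weight gap in safety monitoring. For ALT or AST from 3 to below 8 times ULN, one stand-alone criterion of the immediate-stop rule has no scheduled value at the confirmatory draw. For confirmed 3 to 5 times ULN the first scheduled INR comes nominally 4 to 5 daily doses later (range 2 to 7); for 5 to below 8 times ULN no first day is fixed. The number of subjects with an isolated INR above 1.5 is not given in the documents; near zero is a judgement resting on the absence of Hy's law cases and liver failure in Section 3.4. At 8 times ULN or more there is no gap, because the drug stops regardless. The case for change rests on the low cost of making the rule measurable when it first applies, not on expected harm.

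**What to change.** In Appendix 10, 1.1, replace the exclusion with a requirement for one local-laboratory INR tube at the confirmatory draw (before Day 2) when ALT or AST is at least 3 and below 8 times ULN, including when the repeat enzymes go to the central laboratory. This also fixes a first INR day for the 5 to below 8 band. No INR is needed for the stop decision at 8 times ULN or more. If the later INR is intended, one sentence giving the reason would do instead.

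Costs:

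- one wording change in an amendment, with an ethics committee opinion if the amendment is substantial (Section 12.3)
- one extra tube for the few subjects at this level, including some whose repeat falls below the threshold
- an occasional separate local shipment when the repeat goes to the central laboratory
- a transient raised INR that would have normalised by Day 5 would now stop the drug, as the rule already says.

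### Appendix 10: for a baseline ALT or AST above 2.5xULN, the confirmation level of twice baseline exceeds 5xULN, so no repeat inside the 3.5-5xULN band written for those subjects can open its follow-up

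*Combined protocol and SAP*

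**What the plan says.** Appendix 10 section 1 contemplates subjects with baseline ALT or AST between 2 and 3 times "the ULN, who may be enrolled in the study". Returning subjects are excluded at 3xULN or more (Exclusion Criteria for returning subjects, item 17), so they can restart just below that level.

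Section 1.1 applies once either enzyme reaches 3xULN. A repeat is taken before Day 2, and there are two ways to confirm:
- Scenario 1, normal baseline: "In case Baseline value was within normal range and ALT or AST is still" at or above 3xULN.
- Scenario 2, raised baseline: "In case Baseline value was above ULN and ALT or AST is ≥ 2 times the Baseline value".

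Two things then depend on confirmation. The serology and ultrasound work-up is introduced by "Upon confirmation of the abnormality as noted above, the following additional evaluations should be performed". The monitoring block is headed "Observation and Follow-Up (to be performed after the abnormality was confirmed as above". Within that block:
- Section 1.1.1 covers 3-5xULN, with panels on days 5, 8, 14 and 28. It carries a variant for high baselines: "if Baseline value is $\geq 2.5 \times$ ULN, ALT or AST $\geq 3.5 \times$ ULN and $\leq 5 \times$ ULN".
- Section 1.1.2 covers 5 to below 8xULN: liver tests, blood count "and INR should be monitored twice a week".

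Section 7.3.4.1.1 requires this guidance to be followed closely. It also stops study drug when ALT or AST stays at 5 to below 8xULN on repeated measurements for two weeks or more.

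**The concern.** Section 1.1.1 sets a band for subjects with high baselines, but the confirmation rule ahead of it asks those same subjects for a value above the top of the band. Read literally, a subject with baseline 2.75xULN and a repeat of 4.5xULN is inside the written band, yet gets no scheduled panels, serology or ultrasound.

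The same rule affects a stop. The two-week rule needs repeated measurements, and the twice-weekly tests of 1.1.2 supply them. A high-baseline subject whose repeat is just above 5xULN does not enter that schedule.

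Visit spacing adds to the stakes. After Month 24, scheduled visits are 6 months apart (Tables 7 and 12). Without confirmation, the next scheduled liver panel could be months away. For a returning subject who restarts drug, that interval matches the period in which Section 3.4.1.1 says elevations generally occurred.

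**Working it through.** The plan states no figure to reproduce. The check compares two rules, with all values in multiples of ULN.

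**Inputs**
- Baseline b: up to 3.0 (Appendix 10 section 1); below 3.0 for returning subjects (item 17).
- Confirmation level when baseline is above ULN: c = 2b (section 1.1, scenario 2).
- Band in 1.1.1 for b of 2.5 or more: 3.5 to 5.0 inclusive.
- Band in 1.1.2: 5.0 to below 8.0.

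**Step 1: when can a repeat r be both in the 1.1.1 band and confirmed?** It needs max(3.5, 2b) <= r <= 5. No such r exists when 2b > 5, that is, when b > 2.5.

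**Step 2: which repeats reach 1.1.2 levels unconfirmed?** Those with 5 <= r < 2b. The width is 2b - 5, which is at most 1.0 (at b = 3.0).

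| Baseline b | Confirmation level 2b | Confirmed part of 3.5-5.0 | Unconfirmed part of 1.1.2 band |
|---|---|---|---|
| 2.50 | 5.00 | 5.00 only | none |
| 2.51 | 5.02 | none | 5.00 to <5.02 |
| 2.75 | 5.50 | none | 5.0 to <5.5 |
| 3.00 | 6.00 | none | 5.0 to <6.0 |

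On a grid of 0.01xULN, with baselines 2.51 to 3.00 (50 values) and repeats 3.50 to 5.00 (151 values), 0 of 50 x 151 = 7550 combinations meet the confirmation rule. At baseline exactly 2.50, 1 of 151 does. These are ranges of enzyme values, not shares of subjects.

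**Step 3: does it matter which value sets the band?** The text does not say whether the first or the repeat value does. If the first does, a first value of 4.0 at b = 2.75 still needs a repeat of 5.5 or more. The conflict stands on either reading.

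**Step 4: rise over baseline needed under the proposed wording.**
- At 3.5xULN: 3.5/3.0 = 1.17 (17%), 3.5/2.75 = 1.27 (27%), 3.5/2.5 = 1.40 (40%).
- At 5xULN: 5/3.0 = 1.67 (67%), 5/2.75 = 1.82 (82%), 5/2.5 = 2.00 (the present rule).

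**The case against.** The strongest reply is that the text does not forbid follow-up and that much of the protection needs no confirmation. That is largely right. These remain:
- the liver-focused history and examination, with alcohol avoidance, at 2xULN or more;
- the repeat before Day 2;
- the Section 7.3.4 duty to repeat and follow clinically significant laboratory changes, although it gives no interval;
- unscheduled visits for laboratory follow-up or symptoms;
- confirmation through the other enzyme, if that one was normal at baseline;
- the stops at 8xULN and at 3xULN with raised INR, bilirubin or symptoms. INR is left out of the confirmatory sample only; otherwise, "in case a blood sample is sent to a local laboratory, the following assessments [and reference ranges] are mandatory", and INR is on that list.

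A subject confirmed above 5xULN who later falls into 3.5-5xULN is also already in follow-up. So a reader who infers that the whole search for a cause is withheld, or that liver monitoring ends, goes too far. What is lost is the scheduled panels, the serology and the ultrasound.

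The follow-up sections also open by describing the preceding procedures as required for any elevation above 3xULN. This suggests that the gate was not meant to exclude these subjects. It supports calling this a drafting conflict, but the confirmation condition is still printed.

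Two wider inferences do not hold. One is that the rule is also wrong for baselines of 1.5 to 2.5xULN, where only part of the 3-5xULN band can be confirmed. Requiring a doubling from a raised baseline is a coherent clinical rule, and the band stays reachable. The other is that, for baselines above ULN but below 1.5xULN, a confirmed repeat under 3xULN has no follow-up. That assumes the repeat sets the band, which the text does not say. It also overlooks the monthly central-laboratory minimum in 1.1.1, which for raised baselines applies to abnormalities persisting at 2xULN or more.

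**Conclusion.** The conflict is real for a baseline ALT or AST above 2.5xULN and up to 3xULN. For that enzyme, all of the 3.5-5xULN band and up to 1.0xULN of the next band fail to open their scheduled tests. It should be corrected, because the written rule gives the subjects with the highest baselines less scheduled monitoring than the bands intend for them.

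The reach is probably small. Section 21.1 reports 110 ongoing subjects at Amendment 10, and elevations generally came within 6 months of starting treatment. The documents give no count of raised baselines. Appendix 10 also does not say which baseline is meant (core study, extension or re-enrollment); this affects who is concerned, not the arithmetic.

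**What to change.** Add to scenario 2 that a repeat also counts as confirmed:
1. at 5xULN or more, whatever the baseline; and
2. at 3.5xULN or more, when baseline is 2.5xULN or more.

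The first sentence changes nothing for raised baselines of 2.5xULN or below, where twice baseline is already 5xULN or less. It restores the tests behind the two-week stop. The second makes the special band reachable.

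Align the persistence threshold in 1.1.1 as well. It is now 2xULN for raised baselines, which a baseline of 2.5xULN or more already meets without any rise. For those baselines, 3.5xULN would match the band.

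The cost is a wording change plus a few extra panels, serologies and ultrasounds, some after a modest rise (17% at baseline 3.0xULN). Nobody confirmed today loses confirmation. The second sentence also creates a step at 2.5xULN: a baseline of 2.49 would still need 2 x 2.49 = 4.98xULN, while 2.50 would need 3.5xULN. If that or the 17% is judged unacceptable, the 5xULN sentence alone is enough to protect the stop; 3.5-5xULN would then stay closed for these baselines. The sponsor's safety physicians should approve the final thresholds.
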